9.6.2 Exposure to Investigational Product

The total length of investigational product exposure **and exposure by dose level**, the total dose of investigational product, and the proportion of subjects receiving each dose will be summarized using descriptive statistics.

9.6.3 Exposure to Concomitant Medication

Number and proportion of subjects receiving **acute headache medication or triptan** will be summarized **for baseline and post-baseline.**

9.7 Other Analyses

9.7.1 Analyses of Biomarker Endpoints

Summary statistics will be provided for **baseline** CGRP Biomarker **measurements**.

Endpoints related to **baseline** CGRP **measurements** have been described in Section 9.5.2 and [Tables 7 & 8](#).

10. Changes From Protocol-specified Analyses

The proteomics analyses performed by deCODE are not specified in the protocol but will be performed and included in the final CSR.

The primary endpoint analyses have evolved based on deCODE's recommendation. We will no longer present summaries for any genetic variant that is found to be statistically associated with a 50% reduction in MMD over months 4, 5, and 6. Instead, we will only consider associations for a pre-determined set of genetic variants, where these genetic variants will be selected because they have shown genome-wide significant association with migraine in previous studies (~135 SNPs total expected). The reasoning for this change is that the Bonferroni threshold to determine statistical significance will be stricter if we considered all genetic variants ($0.05/1,000,000 = 5E-8$) than if we only considered a subset of genetic variants (using 135 SNPs gives a threshold of $0.05/135 = 3.7E-4$). This will substantially improve power to detect statistical significance for individual genetic variants.

11. Literature Citations / References

12. Prioritization of Analyses

Prioritization of analyses has not been identified at this time.

13. Data Not Covered by This Plan

The Global Biostatistical Science department will not perform any analyses using genomics or proteomics data in this study and will not analyze post-baseline CGRP data at this time.

14. Appendices

Appendix A. Reference Values/Toxicity Grades

Adverse event severity and laboratory toxicity are graded based on NCI Common Toxicity Criteria version 4.03 or higher, which is available at the following:

https://www.eortc.be/services/doc/ctc/CTCAE_4.03_2010-06-14_QuickReference_5x7.pdf

Appendix B. deCODE Analysis Plan

English: Genetic research methods and data analyses for the Biomarker and Genetic Predictors of Erenumab Treatment Response, a Phase 4 Investigational Open-label Study (INTERROGATE)

Methods and analysis plan:

Whole genome sequencing, genotyping and imputation.

DNA samples will be genotyped using Illumina chips and automated allele-calling software. The front end of the Illumina LIMS system has been integrated with deCODE's blood and DNA sample tracking LIMS system. The data output will feed into deCODE's genotype QC system. We have confirmed the high quality of the data through inheritance checking of large parent-offspring sets. SNPs will be excluded if they have (i) yield lower than 95%, (ii) minor allele frequency less than 1% in the population or (iii) significant deviation from Hardy-Weinberg equilibrium in the controls ($P < 0.001$). All samples with a call rate below 98% will be excluded from the analysis and SNP imputations.

Whole-genome sequencing (WGS) may be performed on selected samples using Illumina technology (1) if they show evidence of rare variants of interest. The sequencing will be performed using NEBNext Ultra™ II DNA Library Preparation and Illumina NovaSeq sequencers.

Sequence variants discovered by deCODE's whole genome sequencing (WGS) project (1) will be imputed. The basis for this imputation is the long range phasing of all chip-genotyped individuals as performed with methods described previously (2,3). Currently, whole genome sequences have been obtained for over 50,000 Icelandic individuals at high coverage of at least 10x (average coverage close to 30x). Sequence variants from these individuals have been propagated using our genealogy and high density genotype databases throughout Iceland's entire population resource. Approx. 36 million variants (SNPs and indels) WGS of ~ 50,000 Icelanders are imputed into >155,000 chip-typed individuals and their first and second degree relatives (1) according to their long range phasing results by the same model as used by IMPUTE (4). For all participants we will impute the SNPs identified and genotyped through sequencing, using imputation assisted by long-range haplotype phasing, the genotypes of all the variants identified by sequencing will be determined for >155,000 Icelanders who have been genotyped with Illumina SNP chips (300K to 2.5 million SNP chips). The nationwide Icelandic genealogical database then allows the propagation of this genotype information into close relatives (for whom we have neither SNP chip nor sequence data) of the chip-genotyped individuals (familial imputation). Such imputed genotypes will be estimated and used temporarily for association analysis, but never stored or made accessible to the researchers.

In addition sequence variants will be imputed from the publicly available SNP data of the HapMap (5) European CEU sample1 (60 triads) and the 1000 Genomes Project data (6) (179 individuals).

Approximately 2.5 million SNPs will be imputed based on the HapMap (6) data, and 6.9 million SNPs based on the 1000 Genomes Project data.

Analysis plan:

Analysis of primary and exploratory objectives will be performed by deCODE. Amgen will provide the subject level clinical endpoints and covariates of interest to be analysed in relation to mPRS, sequence variants, and proteins. The analysis set for all deCODE performed analyses consists of individuals who receive at least one dose of investigational product, have an observed value for the endpoint of interest, pass all quality control procedures, and who are determined to be of Icelandic or Danish ancestry based on admixture analysis. Age, sex, dose switch (yes/no), and the baseline value of the clinical endpoint of interest (when applicable) will be used as covariates in all analyses. Additionally, principal components will be included as covariates in all Denmark related genomic analyses to account for population structure. Analyses will be run both with and without the dose switch (yes/no) and baseline clinical value

covariates to assess model robustness. All described analyses will be run separately in the Iceland and Denmark samples, and subsequently combined in a meta-analysis.

Genomic analyses will focus on a subset of 136 migraine variants found to be associated with migraine in previous literature instead of genome-wide analyses (9, 23). The rationale for focusing on this subset of migraine variants is to substantially reduce the multiple testing burden, since a Bonferroni genome-wide significance threshold = 5E-8 and a Bonferroni corrected threshold for the migraine variant subset = 0.05/136 = 3.7E-4.

Primary objective

To explore the relationship between clinical response to erenumab and genetic/proteomic biomarkers

Endpoint:

Achievement of at least a 50% reduction from baseline in mean monthly migraine days (MMD) over months 4, 5, and 6 in relation to each individual genome-wide significant single-nucleotide polymorphism (SNP) contributing to the migraine polygenic risk score (mPRS).

Method:

Test for association using logistic regression between migraine variants and the mPRS and whether individuals treated with erenumab achieve 50% reduction from baseline in MMD over months 4, 5, and 6. Individuals who do not achieve at least a 50% reduction are considered controls and those who achieve a least a 50% reduction are considered cases.

Additionally, this analysis will be performed separately in each of the following subgroups: sex (female/male), presence of aura during baseline period (yes/no), menstrual-related migraine at screening (yes/no), migraine classification at screening (EM/CM), and prior migraine prophylactic treatment failure (yes/no). The subgroups will be re-examined for appropriateness and may be re-categorized (due to small sample size, for example, if there are < 10% of subjects within a subgroup).

Exploratory objectives

1. To explore the relationship between effect of erenumab on AMSMD and the mPRS

Endpoint: Change from baseline in mean monthly AMSMD over months 4, 5, and 6, in relation to the mPRS

Method:

Test for association between the mPRS and the mean change from baseline in monthly AMSMD over months 4, 5, and 6 using linear regression.

2. To describe the relationship between the mPRS and baseline CGRP

Endpoint: The mPRS in relation to baseline CGRP level

Method:

Test for association between the mPRS and baseline CGRP using linear regression. Association between the migraine SNPs and baseline CGRP will also be analyzed. If high skewness is present, baseline CGRP will be transformed using a log-transformation and rank-based inverse normal transformation to assess model robustness. See Exploratory Objective 1.

3. To describe the relationship between the mPRS and migraine disease characteristics

Endpoints:

- mPRS in relation to baseline MMD
- mPRS in relation to baseline AMSMD
- mPRS in relation to baseline acute headache medication days (AHMD)
- mPRS in relation to Migraine Functional Impact Questionnaire (MFIQ) individual domain scores (physical function, usual activities, social function, and emotional function) and overall impact usual activities global item score at baseline
- mPRS in relation to presence of aura during baseline
- mPRS in relation to baseline mean migraine severity

Method:

Test for association between the mPRS and baseline migraine disease characteristic endpoints using linear regression. See Exploratory Objective 1.

4. To describe the relationship between change from baseline in MFIQ score and mPRS in erenumab treated subjects

Endpoint: Change from baseline in MFIQ individual domain scores (physical function, usual activities, social function and emotional function) and overall impact usual activities global item score at month 6, in relation to mPRS

Method:

Test for association between the mPRS and the specified MFIQ endpoints using linear regression. See Exploratory Objective 1.

Methods:

Association analysis and meta-analysis.

Genomic associations will only be assessed for SNPs previously validated as being genome-wide associated with migraine. This comprises 136 SNPs to date (9, 23), and this list will be updated with any additional migraine SNPs that may be published at the time of analysis. Associations will be assessed separately in each sample (Iceland, Denmark) and then combined in a meta-analysis. A Bonferroni correction will be used to account for multiple testing.

Calculation of migraine polygenic risk scores (mPRS)

Complex traits such as migraine, are affected by many genes and sequence variants, most of which have a small effect on disease risk (8,9). Polygenic scores can be constructed for any complex genetic phenotype for which a GWAS is available, such as from the large migraine GWAS meta-analyses by Gormley et al. including 375,000 individuals (8) and the most recent, even larger (approximately 1 million individuals) by Hautakangas et al (9). The migraine polygenic risk score (mPRS) will be calculated using migraine GWAS summary statistics from the largest cohorts available to deCODE genetics at the time of analysis (excluding data from Denmark and Iceland). The polygenic risk score (mPRS) values can then be calculated for the individuals participating in the clinical trial by summing their identified risk alleles, which are weighted by effect sizes derived from the GWAS results (8). Linkage disequilibrium will be accounted for using the LDpred software package (10). Principal components will be used to account for population structure within Denmark. No overlap between training and testing datasets is essential to maintain independence of predictions, and the removal of related individuals is also needed, as demonstrated and described in detail by Wray et al. (11).

Effect of sequence variants on levels of plasma proteins and CGRP.

Proteins (n=~7,000) in plasma samples from the study participants will be measured using SomaLogic® (SomaLogic, Inc.) as described elsewhere (16,17). In short, aptamers are modified to recognize specific

proteins and an assay quantifies them on a DNA microarray after the protein concentrations are converted into DNA aptamer concentrations. We will perform a proteome-wide association study (PWAS) and evaluate whether migraine associating sequence variants associate with protein levels, after taking into account other pQTLs at the locus that could be driving the signal. Statistical analyses (PWAS) will be performed using linear regression of log-transformed protein levels against erenumab-response, SNP allele count and mPRS. A Bonferroni correction will be used to account for multiple testing.

CGRP will be measured by Meso Scale Diagnostics (MSD). Association of baseline CGRP levels with migraine SNPs and mPRS will be tested.

The ethics of extensive genetic testing

Extensive genetic testing (GWA chip analysis and genome sequencing) is used to assess common complex diseases, i.e., migraine in this study, where the individual risk variant is neither sufficient nor necessary to cause disease. The research results of the extensive genetic testing are therefore important at the group level for scientific purposes, but not valid for making clinical judgments on the individual level on the health of the participants. The research participants will, in general, not be informed of the results of their genetic makeup apart for incidental findings (see below).

Incidental findings

The Infinium® Global Screening Array (GSA) from Illumina® includes a large number of clinically relevant variants (derived from ClinVar, CPIC and PharmGKB) and whole genome sequencing using the Illumina HiSeqX sequencer together with imputation may detect most clinically relevant variants. Therefore, clinically important variants included on the list of genes defined by the American College of Medical Genetics and Genomics (ACMG) that are well studied and would require feed-back to the research participants could incidentally appear in the analysis of genetic associations to specific traits within this study. Because it is not the purpose of these studies to find these variants, detection of these variants will be considered an incidental finding (21).

In the unlikely event that we find a known disease-specific mutations with high penetrance even though it is not part of the specific purpose of the study, we have established an independent committee that will advise us on how to confirm that the mutation is indeed present (confirmation analysis by use of a CE marked assay, see the recommendations given by the National Scientific Ethics Committee doc. no.: 228077, November 2016). The committee will include clinical immunologists, bioinformaticians and molecular biologists. [name], chief physician, professor from the Department of Clinical Genetics at Rigshospitalet will also be part of the committee. If technically validated, the committee will carefully assess the level of evidence for pathogenicity. This will be done using all available literature and exome sequence databases of variants seen in the control population. Such a careful assessment is necessary as recent studies have indicated that many variants have erroneously been reported as pathogenic in monogenic diseases, caused by biased study designs (22). If a mutation is found within the ACMG actionable disorder panel, the participant will be contacted by the research group, provided the participant had previously provided consent.

Contact to the participants with information on incidental findings

For research participants that have a confirmed clinical relevant genetic variant as an incidental finding, the expert committee will appoint a doctor within the specific speciality in the region of the research participants to take care of the clinical management. It is arranged that the research participant has an appointment at the specialist department before the research participant is contacted by phone by the project manager. Only research participants that have agreed to be contacted in case of incidental findings will be contacted. The contact by phone will confirm the research participant's current stance on feedback on genetic findings and will inform the research subject about the finding and the immediate handling of

this. If the research participant agrees to further clinical treatment for the finding he/she will immediately be scheduled for an appointment at the specialist department. At this stage, it will be obvious for the research participant that we have a significant genetic finding. However, the research participant will be offered time for consideration whether he/she wants to be told what the specific genetic finding is – and what it means. If the research participant wants the information – at the same telephone consultation – or at a later consultation – the precise information is given, and the further clinical managements will be in accordance with the management offered for the specific genetic finding. The research participant will be given a phone number on which the project manager can be contacted in case of questions. The research participant will also be offered to invite a representative (e.g. a family member or a friend) to participate in the consultation at the hospital or at telephone conference. At the consultation at the hospital specialist department, the research participant will be given thorough genetic counselling including information about the general knowledge about genetic aetiologies in many diseases and the clinical application of such findings and ethical and legal aspects will be addressed. The research participant will be told about the potential use of genetic findings including the options in relation to work-up of families with inherited diseases. The research participant's rights to know and rights not to know will be discussed.

References

1. Gudbjartsson, D.F. et al. Large-scale whole-genome sequencing of the Icelandic population. *Nat Genet* advance online publication (2015).
2. Kong, A. et al. Detection of sharing by descent, long-range phasing and haplotype imputation. *Nat. Genet.* 40, 1068–1075 (2008).
3. Kong, A. et al. Fine-scale recombination rate differences between sexes, populations and individuals. *Nature* 467, 1099–1103 (2010).
4. Howie BN et al. A flexible and accurate genotype imputation method for the next generation of genome-wide association studies. *PLoS Genet.* 2009;5(6):e1000529 (2009).
5. International HapMap Consortium. A haplotype map of the human genome. *Nature* 437, 1299–1320 (2005).
6. Durbin, R.M. et al. A map of human genome variation from population-scale sequencing. *Nature* 467, 1061–1073 (2010).

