9.3.2.2 Efficacy Analyses

Endpoint	Statistical Analysis Methods
Primary	A GWAS of Icelandic and Danish data will be performed using logistic regression for binary phenotypes. Assuming an additive model, GWAS will be performed for overall sample and by pre-specified subgroups, in addition to other phenotypes of interest that may be defined from the study data. Age and sex will be used as covariates in Icelandic associations and age, sex, and 10 principal components will be used as covariates (to account for population structure) in Danish data. Linkage disequilibrium (LD)-score regression will be used to account for inflation in test statistics due to cryptic relatedness and stratification. A likelihood-ratio test will be used to compute all P-values. The Icelandic and Danish GWAS will be meta-analyzed using a fixed effects model. Weighted Bonferroni adjustment will be used to maintain a family-wise error rate of 0.05 (2-sided) for primary endpoint. Using summary statistics from these studies (excluding GWAS data from Denmark and Iceland), migraine polygenic risk scores (mPRS) will be calculated for the individuals participating in the clinical trial by summing their identified risk alleles, weighted by effect sizes and accounting for linkage disequilibrium using the LDpred software package. This analysis is planned to be performed by deCODE and details of the analysis are described in deCODE Analysis Plan (Appendix B of the statistical analysis plan).
Exploratory	The analyses will be described in the statistical analysis plan, which will be finalized before database lock.

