3.2 Sample Size

The primary objective is the identification of genome-wide significant SNPs contributing to the mPRS that are significantly associated with clinical response to erenumab treatment (based on achievement of at least a 50% reduction from baseline in mean MMD over months 4, 5, and 6). Based on erenumab pivotal EM and CM studies, the $\geq 50\%$ response rate with respect to MMD reduction is expected to be approximately 50% after 24 weeks of erenumab treatment. It is hypothesized that the mPRS SNPs with genome-wide significance ($p < 5 \times 10^{-8}$) have an additive effect on clinical response, ie, for each of these mPRS SNPs, each additional copy of the allele (with 0 as the reference) is associated with increased clinical response and will result in an odds ratio of 1.8 or higher (allelic odds ratio). **Given the currently known 123 migraine SNPs with genome-wide significance and a minor allele frequency (MAF) of at least 0.1, a study of 1400 subjects with 10% dropouts (resulting an effective sample size of 1260 at week 24) is at least 90% powered to identify five of the genome-wide significant migraine SNPs that are statistically significantly associated with clinical response. This is based on a two-sided power analysis, with Bonferroni adjustment, bootstrapping the data from the pivotal EM Study 20120296 ([Mikol et al, 2020](#)), using a logistic regression model to predict clinical response with each SNP, and adjusting for sex, age, BMI and principal components.**

4. Covariates and Subgroups

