4.1 Planned Covariates

All models will be adjusted for age and sex. In addition, all model-adjusted analyses of efficacy endpoints assessing change from baseline will include the corresponding baseline value for the endpoint being analyzed. All models that compare baseline measurements only will be adjusted for country. However, country will not be included as a covariate in any deCODE performed analyses since all deCODE analyses will be performed separately by country (Denmark/Iceland) and subsequently combined in a meta-analysis. Due to the high correlation between baseline dose and country, models assessing change from baseline will instead be adjusted for baseline dose (70mg/140mg) and dose switch only.

Principal components of genotype data will be adjusted for population stratification in mPRS related analysis. Calculation of principal components data will be described in the analysis plan developed by deCODE.

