5.5 Subject Disposition

Exposed to Investigational Product

Subjects are defined as exposed if they receive at least one dose of investigational product. Subjects will be defined as having received IP if the observed data indicates they have received IP (IP date is non-missing) on a specific date, even if the IP quantity field is missing (IPQTY = NULL).

Completing the Investigational Product

Subjects are defined as completing investigational product if they complete IP at week 20. It will be derived from the End of IP eCRF with “Completed” as the primary reason for ending IP.

Completing Study

Subjects are defined as completing study if they complete the entire 24 weeks of study evaluation. It will be derived from the End of Study eCRF with “Completed” as the primary reason for ending study.

On-study

Subjects are considered on-study if they are enrolled and have not yet completed their EOS visit.

Dose Switch

Per protocol, dose switch is permitted at the discretion of the investigator at week 12. However, subjects could switch dose before or after week 12 if needed (e.g., adverse event). We define dose switch as an indicator variable indicating is a subject's dosage changed from their baseline dose at any time during the study.

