Baseline AMSMD in relation to baseline CGRP level	
1. Summary statistics using observed data.2. Estimated slope for CGRP, associated 95% CI and nominal p-value from a linear regression model including age, sex, country (full sample analysis only), and baseline CGRP value as covariate using observed data.3. Spearman correlation between baseline CGRP and baseline AMSMD.
Baseline AHMD in relation to baseline CGRP level	
1. Summary statistics using observed data.2. Estimated slope for CGRP, associated 95% CI and nominal p-value from a linear regression model including age, sex, country (full sample analysis only), and baseline CGRP value as covariate using observed data.3. Spearman correlation between baseline CGRP and baseline AHMD.
Baseline mean migraine severity in relation to baseline CGRP level	
1. Summary statistics using observed data.2. Estimated slope for baseline CGRP, associated 95% CI and nominal p-value from a linear regression model including age, sex, country (full sample analysis only), and baseline CGRP as covariate using observed data.3. Spearman correlation between baseline CGRP and baseline mean migraine severity.
Presence of aura during baseline in relation to baseline CGRP level	
1. Summary statistics using observed data.Estimated odds ratio for baseline CGRP, associated 95% CI and nominal p-value from a logistic regression model including age, sex, country (full sample analysis only), and baseline CGRP using observed data.
Each MFIQ individual domain score (physical function, usual activities, social function, and emotional function) and overall impact usual activities global item score at baseline in relation to baseline CGRP level	
1. Summary statistics using observed data.2. Estimated slope for baseline CGRP, associated 95% CI and nominal p-value from a linear regression model including age, sex, country (full sample analysis only), and baseline CGRP as covariate using observed data.3. Spearman correlation between baseline CGRP and baseline MFIQ score.

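### SAP Appendix B, read literally, adjusts the baseline-only deCODE models for dose switch, a later event; the run that decides the primary SNP test also needs a label.

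*SAP*

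**What the plan says.** **Appendix B.** After naming age and sex, the deCODE plan states that "dose switch (yes/no), and the baseline value of the clinical endpoint of interest (when applicable) will be used as covariates in all analyses". The limiting phrase about applicability is attached to the baseline value, not to dose switch. The plan then adds: "Analyses will be run both with and without the dose switch (yes/no) and baseline clinical value" covariates, giving model robustness as the reason. Its exploratory objectives include baseline-only questions. One is mPRS, and the migraine SNPs, against baseline CGRP. Another covers baseline MMD, AMSMD, AHMD, MFIQ, aura and severity: "Test for association between the mPRS and baseline migraine disease characteristic endpoints using linear regression".

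**Definition.** SAP 5.5 makes dose switch an indicator that the "dosage changed from their baseline dose at any time during the study".

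**SAP 4.1.** Models that compare baseline measurements only are to be adjusted for country, which is left out of deCODE models because these run by country. By contrast, "models assessing change from baseline will instead be adjusted for baseline dose (70mg/140mg) and dose switch only".

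**SAP Table 8.** The sponsor's own models of baseline endpoints on baseline CGRP contain no dose switch. For AMSMD and AHMD the entry is a "linear regression model including age, sex, country (full sample analysis only), and baseline CGRP value as covariate using observed data".

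**Primary test.** Protocol 9.3.2.2 says: "Age and sex will be used as covariates in Icelandic associations and age, sex, and 10 principal components will be used as covariates" in the Danish data. Protocol 9.2.2 adds the baseline value to all model-adjusted efficacy analyses. The power calculation in SAP 3.2 was made "using a logistic regression model to predict clinical response with each SNP, and adjusting for sex, age, BMI and principal components". SAP section 10, on changes from the protocol, does not mention dose switch.

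**The concern.** A confounder of an association between two baseline quantities must act on them. A dose change made weeks later cannot, so adjusting for it removes no bias. It can add bias: if mPRS and the baseline value both influence who switches, they become correlated within switchers and within non-switchers even when they are unrelated in the whole sample. A non-zero slope could then be reported as a link between genetic load and disease severity.

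The second matter is smaller. The SAP calls all analyses descriptive, yet SAP 9.1 sets a family-wise error rate of 0.05 for the primary endpoint and SAP 9.5.1 speaks of identifying significantly associated SNPs. Appendix B plans more than one run per SNP and gives the threshold 0.05/136 without tying it to a run. It does not say whether dose switch and the baseline value are dropped together or one at a time.

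**Working it through.** **1. The plan's own figure.** 0.05/136 = 3.68E-4, which rounds to the stated 3.7E-4. The effective sample size also reproduces: 1400 × 0.9 = 1260.

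**2. Covariates side by side.**

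| Model | Source | Dose switch? |
|---|---|---|
| Baseline endpoint on mPRS or SNP (deCODE) | Appendix B | Yes, read literally |
| Baseline-only models, general rule | SAP 4.1 | Not assigned |
| Baseline endpoint on baseline CGRP (sponsor) | Table 8 | No |
| Change-from-baseline models | SAP 4.1 | Yes |
| Primary SNP test | Protocol 9.3.2.2 with 9.2.2 | No |
| Primary SNP test | Appendix B | Yes, plus runs without |

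The first row is the only baseline-only model with dose switch.

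**3. Size of the induced association (illustration).** From the documents: n = 1260 and two countries analysed separately, then combined. Assumed: equal countries (630 each); switching in one country only; switch probability p = 0.2; correlation of the liability to switch with mPRS r1 = -0.05, -0.1 or -0.2, and with the baseline value r2 = 0.3; no true association between mPRS and the baseline value.

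- Cut-off t = 0.842, normal density φ(t) = 0.280, so k = φ(t)²/[p(1-p)] = 0.0784/0.16 = 0.490.
- Covariance given switch status = -r1·r2·k.
- Partial correlation = -r1·r2·k / √[(1 - r1²k)(1 - r2²k)].
- Expected z of the combined test, with the shift in one country of 630: z = partial r × 630/√1260.
- Type I error at nominal 5% = Φ(-1.96 + z) + Φ(-1.96 - z).

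| r1 | Covariance | Partial r | z | Type I error |
|---|---|---|---|---|
| 0 | 0 | 0 | 0 | 5.0% |
| -0.05 | 0.0073 | 0.0075 | 0.13 | 5.2% |
| -0.1 | 0.0147 | 0.0151 | 0.27 | 5.8% |
| -0.2 | 0.0294 | 0.0304 | 0.54 | 8.4% |

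A large simulation at r1 = -0.2 gave a partial correlation of 0.031, in line with 0.030. Baseline models may keep subjects who later drop out. With all 1400, z in the last row is 0.0304 × 700/√1400 = 0.57 and the error 8.8%.

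**4. Primary test.** One run over 136 independent null SNPs gives 1 - (1 - 0.05/136)^136 = 4.9%. This holds for whichever run is fixed in advance as deciding.

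**The case against.** **The clean estimate will exist anyway.** Appendix B plans every analysis without dose switch too, and these endpoints are exploratory. That limits the harm. It does not repair the model that the text presents as standard, and a reader who sees two slopes is not told which answers the question.

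**SAP 4.1 does not forbid dose switch in baseline-only models.** Correct. It assigns the covariate to the other class of model. The documents are inconsistent, but no express prohibition is broken.

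**The primary test already reads as a main run plus a robustness check.** This largely stands. What is missing is a label next to the threshold, and an entry in section 10, because the protocol's list has no dose switch. Dropping the baseline value would itself depart from Protocol 9.2.2.

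Three stronger readings are tempting, and the documents do not support them:

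- *That family-wise error is inflated.* If a hit in either run counted, it would be about 5.7% to 6.5% when only dose switch differs and 6.8% to 7.8% when the baseline value is dropped too (assumed correlations between the two test statistics of 0.994 to 0.972 and 0.962 to 0.900). No passage states an either-run rule, and the robustness wording points the other way.
- *That type I error in the baseline-only models reaches 8.3% to 19%.* For r1 of -0.1 to -0.2 this needs switching in both countries. SAP 4.1 reports a high correlation between baseline dose and country, and Table 8 drops dose switch for the 140 mg group. Both suggest that switching is concentrated in one country.
- *That dose switch must leave the primary model.* SAP 4.1 chose it for change-from-baseline models. At a minor allele frequency of 0.1 and odds ratio 1.8, illustrative power falls from 75% to 71% or 63% with adjustment if 40% or 70% of early non-responders in one country switch without benefit. It rises from 54% to 65%, or from 39% to 53%, if switching turns 80% of them into responders. The documents do not say which applies.

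**Conclusion.** The point holds for the baseline-only deCODE models. As written they condition on a later event, which cannot reduce confounding and may induce an association, and they depart from SAP 4.1 and from the sponsor's parallel models. The likely size is modest: 5.2% to 8.4% type I error at a nominal 5% under the stated assumptions, and none if switching is unrelated to mPRS or to the baseline value. The switch rate and both correlations are assumed, since the documents give none of them.

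For the primary SNP test the finding is a request for clarity: the adjusted run is implied as main, but this is not stated, and the departure from the protocol's covariate list is not recorded. It is not a finding of lost error control, nor that adjusting for dose switch is wrong there.

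**What to change.** 1. In Appendix B, limit dose switch to models with a post-baseline endpoint and remove it from all baseline-only deCODE models: mPRS and SNPs against baseline CGRP, and mPRS against the baseline disease characteristics.
2. Before database lock, state which single run of the primary test is judged at 0.05/136. Label the other runs as sensitivity analyses, each changing one covariate at a time.
3. If dose switch stays in the deciding model, list it in SAP section 10 as a change from Protocol 9.3.2.2.

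Because dose switch can follow early response, a deciding model with pre-treatment covariates only (age, sex, principal components in Denmark, baseline MMD) is a reasonable option. Its effect on power can go either way, so the choice is the sponsor's.

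The cost is a few lines of SAP text. Runs with and without the covariates are already planned, and no new data are needed. Changing one covariate at a time may add a run per SNP.
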